4.2.3. Sensitivity analyses

Sensitivity analysis will be conducted using a MMRM with the covariates of smoking status, CAT score at baseline, visit, the interaction of CAT score at baseline*visit to derive the point estimate and the standard error of change from the baseline in the CAT score, but in which the

missing data in the primary endpoint will be imputed using monotone linear regression multiple imputation under missing at random assumption, for participants with no intercurrent events, receiving other COPD maintenance therapy, with treatment discontinuation, separately if data permits, otherwise may be imputed for the pooled groups, using the observed factors, i.e. the baseline covariates and the post-baseline covariates by the time of missingness.

The missing values in the covariate may be imputed with information by time of its missingness if deemed necessary.

At least 1000 datasets will be generated which include both observed and imputed values for the covariates. The MMRM estimates for the primary endpoint as well as the corresponding standard errors from each complete dataset will be combined using the Rubin's rule.

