3.7.2 Sample size consideration

A sample size of 460 is planned. With the aforementioned assumptions in [Table 1](#), the sample size would be able to provide a half-width ranging from 0.64 to 0.73 for the 95% confidence interval (CI) of the inverse probability weighted mean of the change from baseline in CAT score at week 12 in the primary analysis under different missingness scenarios ([Table 3](#)).

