Sensitivity analysis will be conducted using the arithmetic mean. Missing data will be imputed using multiple imputation under missing at random assumption, for participants with no intercurrent events, receiving other COPD maintenance therapy, with treatment discontinuation, separately if data permits, otherwise may be imputed for the pooled groups.

Subgroup analyses of the primary endpoint will be further investigated across the CAT score at baseline: moderate impact [CAT 10-20], severe impact [CAT 21-30], very severe impact [31-40].

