4.2.2. Main analytical approach

Primary analysis will be conducted using an inverse-probability weighted mixed model for repeated measures (MMRM) for the change from baseline in CAT score under the missing at random (MAR) assumption to handle missingness which may occur during the data collection.

The inverse probability weighting (IPW) method can reduce the selection bias caused by the missingness, by weighting the participants whose change from baseline of CAT score is observed at week 12 using the inverse probability of completeness in the endpoint. The key assumption for the IPW method is MAR which means that the missingness mechanism of the primary endpoint could be modelled using the observed factors, i.e. the baseline covariates and the post-baseline covariates by the time of missingness, and no unmeasured confounders are involved in the missingness mechanism.

To estimate the probability of the completeness of the primary endpoint, a logistic model is constructed to model its missingness mechanism with the missingness status as the dependent variable (status=observed, status=missing as the reference group). The following baseline and post-baseline covariates will be considered for the missingness of change from baseline in CAT score at week 12:

- Age,
- Gender,
- Years of COPD,
- Smoking history: smoking status and number of pack years,
- Pre-dose FEV1 at baseline,
- COPD maintenance treatment at baseline,
- CAT score at baseline,
- The change from baseline in CAT score at week 4,
- Intercurrent event status: no intercurrent events, received other COPD maintenance therapy, Trelegy discontinued due to other reason.
The subjects receiving other COPD maintenance therapy are those who have discontinued their Trelegy therapy and switched to other COPD maintenance therapy.
- Duration of Trelegy

The right tail of estimated weights may be truncated by its appropriate percentile if deemed necessary.

The change from baseline in CAT score will be analysed using the MMRM model with the covariates of smoking status, CAT score at baseline, visit, the interaction of CAT score at baseline*visit, in which each observation is weighted with the inverse probabilities derived from the above logistic regression models.

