4.8. Changes to Protocol Defined Analyses

Protocol defined that sensitivity analysis will be conducted using the arithmetic mean and missing data will be imputed using multiple imputation under missing at random assumption. The change is that sensitivity analysis will employ a mixed model for repeated measures (MMRM) to estimate the treatment effect. By employing the MMRM model, although the estimate of mean will not change, its standard error may be reduced due to the information from covariates, and the MMRM model provides additional insight to the impact of covariates.

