6.3.2. E.D. Data

To make full use of effectiveness outcomes data, the effectiveness measurements collected at E.D. including CAT score, mMRC and Pulmonary function test (Pre-dosed FEV₁, FVC, FEF₂₅₋₇₅ and IC) will be used according to the following rules:

- If E.D. date of the participant is before Day 55 ($<=55$), the participant's value of week 12 related endpoints will be treated as missing and its analysis approach can be found in Section 4. Otherwise, the participant's value of week 12 related endpoints will be mapped to E.D. results.
- If E.D. date of the participant is before Day 12 ($<=12$), the participant's value of week 4 related endpoints will be treated as missing and its analysis approach can be found in Section 4. Otherwise, the participant's value of week 4 related endpoints will be mapped to E.D. results, if E.D. date of the participant is before Day 21 ($<=20$).

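### The primary analysis and the only sensitivity analysis both assume missing at random (MAR), so MAR, the plan's own key assumption, is never varied

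*SAP*

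**What the plan says.** SAP 4.2.2 makes the primary analysis a weighted MMRM "for the change from baseline in CAT score under the missing at random (MAR) assumption to handle missingness". It names MAR as the key assumption and explains that it requires that "no unmeasured confounders are involved in the missingness mechanism". The weights come from a logistic model. Its covariates include baseline factors, Week 4 CAT change, intercurrent-event status and duration of Trelegy.

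SAP 4.2.3 gives one sensitivity analysis, an MMRM with the same model terms as the primary, after imputation: "missing data in the primary endpoint will be imputed using monotone linear regression multiple imputation under missing at random assumption". Imputation is by intercurrent-event group, "separately if data permits, otherwise may be imputed for the pooled groups".

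Protocol 3.8.2.1 also has a single sensitivity analysis: "Missing data will be imputed using multiple imputation under missing at random assumption". SAP 4.8 declares a change of estimator only, saying that "although the estimate of mean will not change, its standard error may be reduced due to the information from covariates". SAP 4.3.1 and 4.4 carry the same pair of methods to the secondary and exploratory endpoints.

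SAP 6.3.2 decides which early-discontinuation (E.D.) visits count. If that visit falls on or before Day 55, "the participant's value of week 12 related endpoints will be treated as missing and its analysis approach can be found in Section 4". Later values are mapped to Week 12.

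Neither document contains a delta-adjusted, tipping-point, reference-based or other missing-not-at-random analysis.

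**The concern.** Agreement between two MAR analyses is evidence about the weighting and imputation models. It is not evidence about MAR. If participants without a Week 12 CAT score did worse than comparable observed participants, in a way that the recorded factors do not show, both estimates overstate the improvement together.

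Three features of this study make that matter:

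- It is open-label and single-arm with a patient-reported endpoint. The mean change is the result itself, and no control arm exists in which a missingness bias could cancel.
- The planned mean of -1.98 sits almost exactly at the 2-unit minimum clinically important difference (MCID), so a modest bias changes how the size of the effect reads.
- Some late information may go unused. By the SAP 6.3.2 rules, a CAT score from an E.D. visit between Day 21 and Day 55 is assigned to neither Week 4 nor Week 12. It is also not among the listed covariates of the weighting model.

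**Working it through.** **Inputs.** From Protocol 3.7: N = 460 ("A sample size of 460 is planned") and SD 7. The group shares are 79% with no intercurrent event, 20% on other maintenance therapy and 1% discontinued, with mean changes of -2, -2 and 0. Missing proportions in that order are 5/30/50% in Scenario 2 and 10/50/70% in Scenario 3. Delta is **not** in the documents. It is an assumed number of CAT points by which missing participants are worse than MAR predicts.

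**Step 1: reproduce the plan's half-widths.** With π the group share and p the proportion observed, half-width = 1.96 × √{[SD² Σ(π/p) + B]/N}. The between-group variance is B = 0.99 × 0.02² + 0.01 × 1.98² = 0.0396.

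- Scenario 1: Σ(π/p) = 1, half-width 0.640 (stated 0.64).
- Scenario 2: 0.79/0.95 + 0.20/0.70 + 0.01/0.50 = 1.1373, half-width 0.682 (stated 0.69).
- Scenario 3: 0.79/0.90 + 0.20/0.50 + 0.01/0.30 = 1.3111, half-width 0.733 (stated 0.73).

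The figures reproduce, with a difference of 0.008 in Scenario 2. Protocol Table 3 shows an expected mean of -1.98 in every scenario, which is what ignorable missingness within group implies.

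**Step 2: missing share.**

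- Scenario 2: 0.79 × 0.05 + 0.20 × 0.30 + 0.01 × 0.50 = 0.1045, about 48 of 460. Participants with an intercurrent event contribute 0.065.
- Scenario 3: 0.79 × 0.10 + 0.20 × 0.50 + 0.01 × 0.70 = 0.186, about 86 of 460. Participants with an intercurrent event contribute 0.107.

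**Step 3: bias and coverage.** Bias b = delta × missing share. The MAR half-width is held fixed and SE = half-width/1.96, that is 0.348 and 0.374. Coverage = Φ(1.96 - b/SE) - Φ(-1.96 - b/SE).

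| Delta applied to | Delta | Scenario 2: bias, mean, coverage | Scenario 3: bias, mean, coverage |
|---|---|---|---|
| All missing | 2 | 0.21, -1.77, 91% | 0.37, -1.61, 83% |
| All missing | 4 | 0.42, -1.56, 78% | 0.74, -1.24, 49% |
| Missing with an intercurrent event | 2 | 0.13, -1.85, 93% | 0.21, -1.77, 91% |
| Missing with an intercurrent event | 4 | 0.26, -1.72, 88% | 0.43, -1.55, 79% |

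At delta 2 on all missing participants, the 95% interval is -2.45 to -1.09 (Scenario 2) or -2.34 to -0.88 (Scenario 3).

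**Step 4: tipping point.** The upper limit reaches 0 at delta = (1.98 - half-width)/missing share.

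- All missing: 1.298/0.1045 = 12.4 (Scenario 2) and 1.247/0.186 = 6.7 (Scenario 3).
- Intercurrent-event groups only: 1.298/0.065 = about 20 and 1.247/0.107 = 11.7.

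**Step 5: can the discontinued group be imputed separately?** Its expected size is 460 × 0.01 = 4.6, with 2.3 (Scenario 2) or 1.4 (Scenario 3) observed at Week 12. Separate imputation is not realistic, so the pooling fallback is likely. Pooled imputation would draw these participants towards the -2 assumed for the others, although the plan assumes 0 for them.

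**The case against.** The strongest reply is that the plan already deals with most of the problem. The weights use Week 4 CAT change, intercurrent-event status and Trelegy duration, and imputation is by intercurrent-event group where data permit. Participants who visibly worsened are therefore represented. Follow-up continues after Trelegy stops (Protocol 3.2.1), missed visits are chased (3.2.2), and E.D. values after Day 55 are mapped to Week 12. No hypothesis is tested (SAP 2), so no decision threshold is at risk. All of this stands. It narrows the gap to a residual difference beyond the recorded factors, but it does not test for one.

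A reader might also infer more than the documents support:

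- **That the plan expects 30–50% missing among switchers and 50–70% among discontinuers.** These are what-if scenarios for interval width. Scenario 1 has no missing data, and Scenario 3 is labelled the worst case. The 50–70% applies to 1% of participants, about 2 to 3 people.
- **That switchers leave because they feel worse.** Neither document says so. Protocol Table 2 gives switchers the same mean change, -2, as those with no intercurrent event.
- **That the sensitivity analysis duplicates the primary.** One rests on a missingness model and the other on an outcome model, so it does check misspecified or truncated weights. The MMRM terms are shared, but SAP 4.2.3 does not itemise the imputation covariates.
- **That coverage could fall to 49%.** That needs Scenario 3, a delta of twice the MCID, and the same penalty on participants with no intercurrent event. They make up 38% (18.2/48.1) of the missing in Scenario 2 and 42% (36.3/85.6) in Scenario 3.

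**Conclusion.** The point holds in a bounded form. Both analyses assume MAR, and nothing in either document departs from it. At an assumed delta of 2, the mean improvement is overstated by 0.21 (Scenario 2) or 0.37 (Scenario 3) if all missing participants are affected, and by 0.13 or 0.21 if only those with an intercurrent event are. Coverage is then about 91% or 83%, and about 93% or 91%, respectively.

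It would be tempting to conclude that the Week 12 benefit might vanish. The planning figures do not support that. The upper limit reaches 0 only at a delta of about 6.7 to 12.4, or about 11.7 to 20 when limited to intercurrent-event groups, which is more than three times the MCID in every case. The risk is an overstated effect size against the 2-unit MCID and an overconfident interval, not a reversal.

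These sizes rest on the protocol's scenario missingness, its assumed means and SD, a half-width held at its MAR value, and deltas that are illustrative. With little missing data the issue shrinks in proportion. It is a worthwhile and cheap improvement rather than a defect that invalidates the analysis.

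**What to change.** Keep the planned MAR imputation as it is and add to SAP 4.2.3 a pre-specified delta-adjusted analysis on the same imputed datasets (at least 1000), combined by Rubin's rules:

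- Add delta to the imputed Week 12 CAT changes, varied by intercurrent-event group (none, switched to other maintenance therapy, discontinued). As a minimum, show one series with a common delta in all groups and one with delta only in the two intercurrent-event groups. Group membership is known, so this works even if imputation is pooled.
- Extend the grid until the upper 95% limit reaches 0 and report that delta. A grid of 1 to 4 points would stop short of the tipping points above. If the tipping delta is implausibly large on a 0–40 scale, that is itself the reassurance sought.
- Add a return-to-baseline run (mean change 0) for discontinuers, reported separately from switchers, because the plan assumes 0 for the former and -2 for the latter. On the planned mix this moves the mean by only about 0.01 (2 × 0.005 or 2 × 0.007, if pooled imputation had placed them at -2). Its value depends on how many discontinue in practice.
- Show all estimates beside the 2-unit MCID.

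The cost is one SAP paragraph, one table and a loop over existing imputations, with no new data. The downside is that the report will carry a less favourable range of estimates.

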4.3. Secondary Endpoints Analyses

4.3.1. Secondary endpoints

The analysis approach for the below secondary endpoints is analogous to the primary analysis and the sensitivity analyses for the primary endpoint:

- Change from baseline of Modified Medical Research Council (mMRC) at week 12
- Change from baseline of pre-dose FEV₁ at week 12
- Proportion of CAT responder (defined as ≥ 2 unit decrease from baseline) at week 12
- Change from baseline of CAT score at week 4

In the analysis for the proportion of CAT responder (defined as ≥ 2 unit decrease from baseline) at week 12, the considerations follow:

- Summary measure is the proportion of participants having ≥ 2 unit decrease from baseline at week 12.
- The response status of a participant at a visit is set to missing if his/her CAT score at baseline or at the visit is missing.
- The IPW weights used for primary endpoint were applied here to estimate the proportion of CAT responder at Week 12.

The missingness of the change from baseline in CAT score at week 4 will be modelled analogously as the primary analysis but with the covariates collected before week 4. The missing values in the covariates may be imputed with information by time of its missingness. The IPW weights are applied at the observation level, thus the observations for a same subject with available change from baseline in CAT score values at the week 4 and week 12 may have different weights.

4.4. Exploratory Endpoints Analyses

The analysis approaches for the below exploratory endpoints are analogous to the primary analysis and the sensitivity analyses for the primary endpoint:

- Change from baseline of Forced Vital Capacity (FVC) at week 12
- Change from baseline of Forced Expiratory Flow at the 25% and 75% (FEF_{25-75}) at week 12
- Change from baseline of Inspiratory Capacity (IC) at week 12

4.5. Safety Analyses

The safety analyses will be based on the Full Analysis Set, unless otherwise specified.

4.5.1. Adverse Events

AE terms will be coded using Medicinal Dictionary for Regulatory Activities (MedDRA) dictionary.

The number and percentage of participants experiencing at least one AE of below category will be summarized:

- Overview of AEs
- On-treatment AEs will be summarized by system organ class (SOC) and preferred term (PT) for:
 - Trelegy related non-serious AE
 - SAEs
 - Trelegy related SAEs
 - AE leading to discontinuation of Trelegy
 - Trelegy related AE leading to discontinuation of Trelegy
- Post-treatment AEs will be summarized for:
 - SAEs by SOC and PT

4.5.2. Vital Signs and Others

Body Temperature, Pulse Rate, and Blood Pressure (systolic and diastolic) will be summarized at the scheduled time points specified in Visit 1 and Visit 3.

Pregnancy status will be listed if any.

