3.2. Data Source / Data Collection

The investigators will enroll participants by assessing the inclusion/exclusion criteria. The patients will be enrolled at visit 1 and will be followed up prospectively for 12 weeks.

During this trial the following information and measurements will be collected, and the details are listed in [Table 1](#):

To be completed at Visit 1:

- Patient demographics (including sex, age, height, weight)
- Patient past medical history and co-morbid diseases
- Patient smoking history [never a smoker, former smoker (previously smoked ≥ 10 pack year and has not smoked for at least 6 months prior to Visit 1), current smoker (10 pack year and smoked within 6 months prior to Visit 1); the number of pack years for former smoker and current smoker should be calculated (round up to the nearest integer)]
- Patient concomitant medication
- Pregnancy status
- Oxygen saturation
- Patient vital signs and Electrocardiogram (ECG)
- CAT score
- mMRC
- Pulmonary function test (spirometry): pre-dose FEV1, FVC, FEF₂₅₋₇₅ and IC
- Trelegy related AEs
- AEs that lead to the discontinuation of Trelegy
- SAEs

To be completed at Visit 2:

- Patient concomitant medication
- Pregnancy status
- Number of doses of Trelegy taken
- CAT score
- Trelegy related AEs
- AEs that lead to the discontinuation of Trelegy
- SAEs

To be completed at Visit 3 or E.D.:

- Patient concomitant medication
- Pregnancy status
- Number of doses of Trelegy taken
- Patient vital signs
- CAT score
- mMRC
- Pulmonary function test (spirometry): Pre-dosed FEV₁, FVC, FEF₂₅₋₇₅ and IC
- Trelegy related AEs
- AEs that lead to the discontinuation of Trelegy
- SAEs

Table 1 Visit flow chart and data collection schedule

Procedure	Conse nting	Treatment and Observation Period (Days)			E.D.	Notes E.D. = early discontinuation / withdrawal (within 7 days of study discontinuation)
Study visit	V0 ¹ Pre- Scree ning	V1 Screen, enroll & baseline (Day 1)	V2 (Day 28)	V3 End of Study (Day 84)		
Time Window Allowed (days)			±7	±10		
Informed consent ²	X					
Inclusion / exclusion criteria		X				
Demography		X				
Full physical examination including height and weight		X				
Smoking History		X				

Procedure	Conse nting	Treatment and Observation Period (Days)				Notes E.D. = early discontinuation / withdrawal (within 7 days of study discontinuation)
Medical history: past and current medical conditions		X				
Vital signs		X		X	X	
Oxygen saturation		X				
ECG		X				

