3.2.1. Withdrawal from Trelegy or the Study

Participants that permanently stop Trelegy are not required to withdraw from the study. If for any reason a participant must permanently stop Trelegy, every effort should be made by the Investigator/delegate to keep the participant in the study to collect all the effectiveness and safety data of the subsequent visits per the Schedule of Activities (SoA) after the Trelegy discontinuation.

Any female participant who becomes pregnant while participating will be withdrawn from the study.

A participant may withdraw from the study at any time at his/her own request, or may be withdrawn at any time at the discretion of the investigator for safety, behavioural, or administrative reasons. If a participant withdraws from the study, he/she has to complete the E.D. visit per SoA ([Table 1](#)), and no more extra data will be collected after E.D. visit.

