3.6.2.2 Vital signs

Vital signs (Body Temperature, Pulse Rate, Blood Pressure) will be performed at the time points specified in Visit 1 and Visit 3/E.D. prior to conducting spirometry and prior to taking the morning dose of study treatment. Blood pressure (systolic and diastolic) and pulse rate will be measured in the sitting position after approximately 5 minutes rest. A single set of values will be collected and recorded in the source documentation and eCRF.

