6.3. Appendix 3 Assessment Windows

6.3.1. General

In general, data will be reported according to the nominal time of clinic visits and assessments as specified in the protocol.

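### Vital signs collected at the early discontinuation visit enter no planned summary, so the post-baseline vital-signs table covers only participants who reach Visit 3

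*SAP*

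**What the plan says.** **Collection.** Protocol 3.6.2.2 says that vital signs "will be performed at the time points specified in Visit 1 and Visit 3/E.D. prior to conducting spirometry". The visit list in protocol 3.2 puts them under the heading "To be completed at Visit 3 or E.D", and Table 1 marks them at Visit 1, Visit 3 and E.D. The E.D. visit belongs to participants who leave the study (protocol 3.2.1): "If a participant withdraws from the study, he/she has to complete the E.D. visit per SoA". Those who only stop Trelegy are to be followed on to Visit 3.

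**Analysis.** SAP 4.5.2 says that vital signs "will be summarized at the scheduled time points specified in Visit 1 and Visit 3". SAP 6.3.1 adds that, in general, "data will be reported according to the nominal time of clinic visits and assessments as specified in the protocol". SAP 6.3.2 then sets out when E.D. results may stand in for Week 4 or Week 12, but its scope is "the effectiveness measurements collected at E.D. including CAT score, mMRC and Pulmonary function test". Vital signs are not in it, and SAP 4.5.2 specifies no change from baseline.

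**The concern.** A record labelled E.D. stays E.D. unless a rule moves it, and no rule moves vital signs. Pulse and blood pressure taken at a withdrawal visit are therefore collected but not tabulated. The table would set Visit 1 values from the Full Analysis Set beside Visit 3 values from those still in the study. Without a paired change from baseline, the two columns describe different groups of people.

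The treatment of a single visit is also uneven. For a participant whose E.D. visit falls after Day 55, SAP 6.3.2 counts that day's CAT, mMRC and spirometry as Week 12, while the blood pressure from the same visit appears nowhere.

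The table has some weight because Table 1 schedules ECG, oxygen saturation and physical examination at Visit 1 only. Vital signs are the one physiological safety assessment repeated after dosing. They also do not depend on the causality judgement that governs which non-serious adverse events are recorded.

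**Working it through.** **Step 1: the text.**

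| Question | Source | Answer |
|---|---|---|
| When are vital signs measured? | Protocol 3.2, Table 1, 3.6.2.2 | Visit 1, and Visit 3 or E.D. |
| When are they summarised? | SAP 4.5.2 | Visit 1 and Visit 3 |
| How are visits labelled? | SAP 6.3.1 | By nominal visit |
| Which E.D. data are mapped to a scheduled visit? | SAP 6.3.2 | CAT, mMRC, spirometry |

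Taken together, these leave E.D. vital signs in no planned summary.

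**Step 2: check the inputs used for size.** The documents give no missingness for vital signs, so I use the CAT scenarios in protocol Table 3 as a stand-in. Group shares π are 0.79 (no intercurrent event), 0.20 (other maintenance therapy) and 0.01 (discontinued), from protocol 3.7.1. Missing shares m are 0/0/0 in Scenario 1, 5%/30%/50% in Scenario 2 and 10%/50%/70% in Scenario 3. With SD 7.003 and N = 460, the plan's half-width is 1.96 × 7.003 × √(Σ π/(1−m) / 460):

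- Scenario 1: Σ = 1, giving 0.640 (plan: 0.64).
- Scenario 2: Σ = 0.8316 + 0.2857 + 0.0200 = 1.137, giving 0.683 (plan: 0.69).
- Scenario 3: Σ = 0.8778 + 0.4000 + 0.0333 = 1.311, giving 0.733 (plan: 0.73).

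Both ends of the stated range reproduce, so the inputs are read correctly. This point disputes none of those figures.

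**Step 3: participants without a Visit 3 value.**

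- Scenario 2: 0.79×0.05 + 0.20×0.30 + 0.01×0.50 = 0.1045, or 48 of 460. Observed: 412.
- Scenario 3: 0.79×0.10 + 0.20×0.50 + 0.01×0.70 = 0.186, or 86 of 460. Observed: 374.

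**Step 4: E.D. records left out.** Assume that 25-75% of those missing attend an E.D. visit. Low end: 0.25 × 48 = 12. High end: 0.75 × 86 ≈ 64.

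**Step 5: effect on the post-baseline mean.** Assume that pulse at E.D. is 5-10 bpm higher than at Visit 3. Adding the records to those observed moves the mean by:

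- Low end: 12/(412 + 12) × 5 = 12/424 × 5 = 0.14 bpm.
- High end: 64/(374 + 64) × 10 = 64/438 × 10 = 1.5 bpm.

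**Step 6: Trelegy status at Visit 3.** SAP 4.2.2 describes switchers as having stopped Trelegy. On the same shares, the off-Trelegy fraction among those observed is 0.21 in Scenario 1, (0.14 + 0.005)/0.8955 = 16.2% in Scenario 2 and (0.10 + 0.003)/0.814 = 12.7% in Scenario 3.

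**The case against.** **Visit 3 may be shorthand for Visit 3/E.D.** This is possible, since the protocol pairs them. But SAP 4.5.2 speaks of scheduled time points, and SAP 6.3.2 shows that the authors wrote an explicit rule where they wanted E.D. data used. The shorthand reading is not what the text says.

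**The table is secondary.** This stands. The safety outcomes are Trelegy-related AEs, SAEs and AEs leading to discontinuation, and the protocol's safety analysis plans only those. The vital-signs table is an addition in the SAP. SAP 4.1.1 reports n, so the fall in numbers by Visit 3 would be visible.

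**Early leavers are not lost to safety reporting.** This also stands. A reader might infer that the safety evaluation as a whole rests on those who stayed. It does not: SAP 4.5 and 4.5.1 summarise AEs on the Full Analysis Set. A clinically significant vital-sign change can qualify as an AE under protocol 10.1, and AEs leading to discontinuation of Trelegy are recorded whether or not judged related. Only the measured values go untabulated.

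**Direction of bias.** A reader might infer that the omission, together with off-Trelegy values at Visit 3, pushes the table towards no change. The documents do not support this. People may leave at their own request, for administrative reasons or through loss to follow-up. Of the 21 percentage points assumed to have an intercurrent event, 20 are participants who moved to another maintenance therapy, and everyone enters on maintenance therapy, so neither baseline nor Visit 3 is a drug-free comparison. In Scenarios 2 and 3 about 62% and 58% of those missing are off Trelegy, so adding E.D. would itself bring in off-Trelegy values.

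**Conclusion.** The point holds as a gap in one descriptive safety table. E.D. vital signs are collected under the protocol and reach no planned summary, so the post-baseline column describes only participants who reach Visit 3. The primary estimand, the sample size and the AE summaries are unaffected.

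The size is illustrative: about 12 to 64 records, and a shift in mean pulse of about 0.14 to 1.5 bpm. It rests on three assumptions that the documents do not supply: missingness like that of CAT, 25-75% E.D. attendance, and a 5-10 bpm difference. The count could be larger, because a late E.D. visit can count as observed Week 12 CAT while vital signs have no such mapping. It could be smaller, because some missing values will be missed visits with no E.D. attendance.

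A reader might multiply the whole missing fraction by the assumed difference and get 0.5 bpm (0.1045 × 5) to 1.9 bpm (0.186 × 10). That compares the table with one holding values for all participants. Under the stated attendance, many of those values would not exist and no change to the SAP could restore them.

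**What to change.** Amend SAP 4.5.2 to summarise vital signs at Visit 1, Visit 3 and E.D., with n at each. Add the last post-baseline value (Visit 3 or E.D.) with change from baseline in participants who have both values.

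A split by Trelegy status is optional. If made, it should rest on whether Trelegy had been permanently discontinued before the assessment, or on a stated window after the last dose. The cut-off in SAP 6.2.1 should not be used unmodified: it ends the on-treatment period at the last dose date, and vital signs are taken before the morning dose. A completer last dosed the day before Visit 3 would be classed as post-treatment.

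The cost is a change of SAP wording and one extra table from data already collected, with no change to study conduct.
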